Statistical Analysis: A 2(Strategy) X 3(Time) mixed ANOVA will be used to statistically identify significant interactions and main effects for spinal height, pain and function outcome measures. Post-hoc pairwise comparisons will be used to locate significant differences between the different conditions (Time). Significance will be set at $\alpha = 0.05$. Pearson product-moment correlations will be used to measure correlations between lumbar ROM in relation to spinal height and outcome measures. The Kruskal-Wallis 1-factor ANOVA for difference scores will be used to determine changes of intensity and location of symptoms following sustained versus repetitive standing trunk extension. Spearman Rank correlation will be used to evaluate the relationship between spinal height changes and changes of pain and location of symptoms for each group.

Word Count: 326

Key Words: Standing postures; trunk extension; spinal height change; stadiometer

Lay Summary

Standing back extension postures have been used for many years to treat people with low back pain.

No study to date has investigated the effect of standing back extension postures on trunk height, pain and function.

The **purpose** of this study will be to evaluate in subjects with low back pain how trunk height, pain and function respond to standing repetitive versus sustained trunk extension postures.

Methods: A randomized clinical trial will be used to determine how trunk height, low back pain and function change in response to sustained and repetitive standing trunk extension after a period of spinal loading.

Statistical Analysis will be used to measure the outcomes.

LIST OF FIGURES

Figure 1: Flowchart depicting testing sequence.....31

Figure 2: Starting position for standing trunk extension (repetitive and sustained).....34

Figure 3: Sustained trunk extension position and end position of repetitive trunk extension.....35

Figure 4: Position of subject for spinal height measure in stadiometer unit.....36

Figure 5: Position of subject during spinal loading time in sitting.....37

Figure 6: Home exercise program for repetitive trunk extension group.....38

Figure 7: Home exercise program for sustained trunk extension group.....39

Figure 8: Home instructions for each subject.....40

LIST OF ABBREVIATIONS

Analysis of Variance.....	ANOVA
Fear Avoidance Belief Questionnaire.....	FABQ
Intervertebral Disc.....	IVD
Institutional Review Board.....	IRB
Low Back Pain.....	LBP

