function testing outcomes immediately and two weeks following the interventions in patients with LBP.

2. **RH 2:** It is expected that following a period of trunk loading, sustained standing trunk extension posture in standing will result in greater spinal height gain as compared to repetitive standing trunk extension postures, while repetitive standing trunk extension postures will result in greater improvements in pain, centralization and function testing outcomes as compared to sustained standing trunk extension postures immediately and two weeks following the interventions.
3. **RH 3:** It is expected that following a period of trunk loading, there will be a positive correlation between the degree of trunk extension during standing trunk extension posture and spinal height, centralization, pain and function testing outcomes changes immediately and two weeks following the interventions in patients with LBP.

Comparison Variables

Independent Variable(s)-The student plans to use the following Independent variable(s) (IV)

1. IV1: Trunk extension
 - a. IV1: sustained
 - b. IV2: repetitive
2. IV2: Time

- a. IV1: before
- b. IV2: after (immediately)
- c. IV3: after 2 weeks

Dependent Variable(s)-The Student plans to measure the following dependent variable(s) (DV)

1. DV1: Spinal height using stadiometer (ratio scale).
2. DV2: Pain rating using numerical pain rating scale (NPRS) (ordinal scale).
3. DV3: Centralization (ordinal) using body diagram.
4. DV4: Modified Oswestry Pain Disability Questionnaire (ordinal scale)

Relationship Variable(s)- (RV) (if applicable)

1. RV1: Degree of spinal extension (ratio)
2. RV2: Spinal height using stadiometer (ratio scale).
3. RV3: Pain rating using numerical pain rating scale (NPRS) (ordinal scale).
4. RV4: centralization (ordinal).
5. RV5: Modified Oswestry Pain Disability Questionnaire (ordinal scale)

METHODS

Research Design(s)

A pre-test, post-test comparison group design (randomized clinical trial) will be used to determine how spinal height changes in response to sustained and repetitive standing trunk extension after a period of spinal loading. The study will use a 2 (between subjects – type of trunk extension: sustained vs. repetitive) x 3 (within subjects - time: before vs. after vs. 2 weeks after) mixed design to evaluate the effects of sustained and repetitive trunk extension in standing on spinal height, pain, centralization and function outcome measures.

Pre-study Approvals

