changes in spinal height, degrees of spinal extension, pain, and function outcomes.

For *experimental hypothesis 1*, a paired-t-test (or Wilcoxon sign-rank test if the data do not meet assumptions for parametric inferential statistics) will be used to assess differences in spinal height, centralization and pain outcomes improvements following sustained and repetitive trunk extension postures.

For *experimental hypothesis 2*, 2 (between subjects - type of trunk extension: sustained vs. repetitive) x 3 (within subjects - time: before, immediately after and 2-week after) mixed ANOVA's will examine differences in (1) spinal height; (2) pain; and (3) function outcomes, as a result of sustained and repetitive standing trunk extension after a period of spinal loading. Post hoc paired t-tests will explore further for significant differences in spinal height, pain and function outcomes between the six conditions.

Experimental hypothesis 3 will be tested with Pearson product-moment correlations to determine the strength of correlations between the degree of trunk extension during standing trunk extension posture and spinal height, pain and function, outcomes changes in patients with LBP.

Spearman's Rank Order correlation will be used to determine the strength of the correlation between centralization and the degree of trunk extension posture in standing.

Alpha level will be set at 0.05 for significance for all tests and Bonferroni corrections performed as needed.

REFERENCES

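### Hypothesis 2 predicts a between-arm difference in centralization, but Data Analysis gives no test for it. The abstract's test is valid but less efficient than a baseline-adjusted one, and may give pain a second, unranked test

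*Combined protocol and SAP*

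**What the plan says.** The document declares centralization an ordinal dependent variable. It is scored from body diagrams on six levels, a higher score meaning more distal symptoms. Under Research Hypotheses, RH 2 says that "repetitive standing trunk extension postures will result in greater improvements in pain, centralization and function testing outcomes", compared with sustained extension, immediately and at two weeks.

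In Data Analysis (Inferential analyses), the paragraph for hypothesis 2 states that 2 x 3 mixed ANOVAs "will examine differences in (1) spinal height; (2) pain; and (3) function outcomes". The follow-up sentence keeps to the same three outcomes: "Post hoc paired t-tests will explore further for significant differences in spinal height, pain and function outcomes between the six conditions".

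Centralization appears in that section in two other places:

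- Under hypothesis 1, a paired t-test, or a Wilcoxon test if parametric assumptions fail, "will be used to assess differences in spinal height, centralization and pain outcomes improvements following sustained and repetitive trunk extension postures".
- Under hypothesis 3, a Spearman coefficient measures "the strength of the correlation between centralization and the degree of trunk extension posture in standing".

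The abstract's Statistical Analysis paragraph adds: "The Kruskal-Wallis 1-factor ANOVA for difference scores will be used to determine changes of intensity and location of symptoms" after sustained versus repetitive extension. The same paragraph already places pain under another test: "A 2(Strategy) X 3(Time) mixed ANOVA will be used to statistically identify significant interactions and main effects for spinal height, pain and function outcome measures".

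**The concern.** RH 2 makes a directional claim about four outcomes, and the section that governs the analysis supplies an arm comparison for three. An analyst working from Data Analysis alone would have no planned way to answer the centralization part.

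Turning to the abstract raises three further questions. A raw difference on a bounded six-level score does not condition on where the subject started, although the baseline zone is collected and could be used at no cost. The abstract does not say whether the difference is the immediate or the 2-week one. And its sentence also covers symptom intensity, so pain may have two between-arm tests, with nothing to say which is decisive. The result for pain could then be taken from whichever test is more favourable.

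**Working it through.** **1. Which analyses compare the arms on centralization?**

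| Place | Analysis | Compares arms on centralization? |
|---|---|---|
| Data Analysis, hypothesis 1 | paired t or Wilcoxon signed-rank | No, within subject |
| Data Analysis, hypothesis 2 | mixed ANOVA and post hoc tests | No, outcome not listed |
| Data Analysis, hypothesis 3 | Spearman with extension angle | No, association only |
| Abstract | Kruskal-Wallis on differences | Yes |

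So one of the four RH 2 outcomes lacks an arm comparison in Data Analysis.

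**2. Efficiency of a difference score.** The plan gives no power, effect size, SD or pre-post correlation, so there is no figure of its own to reproduce. With two groups, Kruskal-Wallis is the rank-sum test, so any loss comes from the difference score and not from the choice of rank test.

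For a continuous score with unit SD and pre-post correlation r:

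- variance of change = 2(1 - r)
- variance after baseline adjustment = 1 - r²
- relative efficiency of change = (1 - r²) / [2(1 - r)] = (1 + r)/2

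This is one half only at r = 0; it is 0.75 at r = 0.5 and 0.85 at r = 0.7.

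Approximate power is Φ(d√(n/2)/SD - 1.96). Assume n = 20 per arm (the 40 planned completers split equally; the ratio is not stated), d = 0.8, and a two-sided 0.05 level. At r = 0.5:

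- change: SD = √1 = 1; 0.8 × √10 = 2.53; 2.53 - 1.96 = 0.57; power 0.72
- adjusted: SD = √0.75 = 0.866; 2.53/0.866 = 2.92; 2.92 - 1.96 = 0.96; power 0.83

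**3. The same comparison on a six-level score.** This was simulated by cutting correlated latent normals into six zones, with 20 per arm and an arm effect of 0.8 latent SD. Kruskal-Wallis on the difference was compared with ANCOVA on the ranks of the post score, with the ranked baseline as covariate. All baseline shares, correlations and common improvements are assumptions.

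| Baseline and common improvement | r | Difference | Adjusted | Retained |
|---|---|---|---|---|
| Shares 25/20/20/15/10/10%, none | 0.4 | 45% | 68% | 45/68 = 0.66 |
| same | 0.6 | 57% | 77% | 57/77 = 0.74 |
| same | 0.8 | 80% | 91% | 80/91 = 0.88 |
| same shares, 0.4 SD in both arms | 0.4 | 33% | 62% | 33/62 = 0.53 |
| same | 0.8 | 54% | 82% | 54/82 = 0.66 |
| Shares reversed (distal), none | 0.8 | 90% | 93% | 90/93 = 0.97 |
| Floor-heavy, with common improvement | 0.4 to 0.8 | 17-23% | 45-58% | about 0.4 |

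The floor effect can also be seen at r = 0.5 with a 0.5 SD common improvement: with 40% of subjects starting at level 1, power is 21% against 53%; with 60%, it is 12% against 34%. Over a wider grid (r from 0 to 0.85, four baseline distributions) the retained share ran from 0.31 to 0.99, a loss of about 1% to 69%. Type I error stayed near the nominal 5% for both methods.

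**4. Two tests for pain.** If intensity means pain, the mixed-ANOVA interaction and Kruskal-Wallis both compare the arms on it. Two independent tests at 0.05 would give 1 - 0.95² = 0.0975. These tests are correlated. A null simulation (6,000 replicates, correlation 0.3 to 0.7) gave 0.073 to 0.083 for at least one of the ANOVA interaction and Kruskal-Wallis on the immediate change, and 0.097 to 0.107 when Kruskal-Wallis on the 2-week change was added.

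**The case against.** The strongest reply is that a between-arm test for centralization is named in the document, so this is mainly a mismatch between abstract and body. That test is valid: it holds its type I error, suits an ordinal outcome and compares the two arms. The Background also describes centralization as symptoms retreating from distal to proximal, which is a change, so a difference score measures the construct directly. All of this stands. It lowers the severity, but it does not put the test into the hypothesis 2 paragraph, choose a time point or recover the information in the baseline zone.

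Four stronger readings are tempting, and the documents do not support them:

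- A reader might infer that the abstract's test wastes about half the attainable power. That is true only in some scenarios, with weak correlation or many subjects starting at the most proximal level. Leg symptoms are not required at entry and RH 1 expects both arms to improve, so a floor effect is plausible. It is not documented.
- A reader might infer that the difference score ignores baseline. It subtracts baseline; what it does not do is condition on it.
- A reader might infer that centralization falls to the t-test by default under hypothesis 1, because the variables listed for distribution checks end with "changes in spinal height, degrees of spinal extension, pain, and function outcomes" and leave centralization out. But the plan declares the score ordinal, uses rank methods for it elsewhere and allows Wilcoxon in that same paragraph. The omission fits prior non-parametric handling at least as well.
- A reader might take it as certain that pain has two tests. Paresthesia intensity is also collected at both sessions, so intensity in the abstract is ambiguous.

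**Conclusion.** The concern holds in a limited form and should be fixed, though it does not invalidate the trial. From the text alone, without assumptions: RH 2's centralization claim has no arm comparison in Data Analysis, and the one in the abstract is not carried over and has no stated time point.

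The abstract's test is valid but less efficient. Baseline adjustment gave higher power in every baseline scenario tabulated, by margins from 3 points (90% against 93%) to more than 25 points under a floor-heavy baseline with common improvement. The size rests on assumed baseline shares, correlation, effect, equal allocation and a two-sided 0.05 level, none of which the documents supply. It should be quoted only as a conditional range.

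The pain problem is conditional on reading intensity as pain. In that case the unadjusted false-positive chance is about 7-8%, or 10-11% with the 2-week change included. The plan's provision for Bonferroni correction as needed does not settle this, because it defines no family of tests.

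**What to change.** - **Hypothesis 2 paragraph:** add centralization. Compare the post-intervention zone score (1 to 6) between arms by rank ANCOVA, with the session 1 pre-intervention zone score as covariate, immediately after the intervention and at 2 weeks.
- **2-week score:** name the diagram. Session 2 collects one on arrival and another after the repeated intervention, and the text does not say which is analysed.
- **Multiplicity:** apply the plan's Bonferroni correction across the two time points, 0.05/2 = 0.025 each. The powers shown above are at 0.05 and will be lower at this level for either method.
- **Abstract:** remove the Kruskal-Wallis sentence or label it supportive, so that one named test decides for pain. If intensity was meant as paresthesia, say so.
- **Hypothesis 1 paragraph:** state the Wilcoxon signed-rank test for centralization. This is a clarification, since the plan already allows it and declares the score ordinal.

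The cost is a few lines of analysis wording, best settled before outcome data are examined. No new data, visits or measurements are needed.

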(Kourtis 2004; Magnusson 1996; Lazzarini 2014; Simmerman 2011). These studies stem from IVD height preservation in the aging spine. Natural IVD height preservation is so important that the biomedical field has examined the use of growth factors for IVD biologic regeneration (Masuda 2004) in order to more naturally preserve IVD biomechanical and physiological function as opposed to surgical disruption. To further understand IVD functional properties, researchers have studied the IVD hydraulic permeability and the influence that age and/or degeneration have on fluid movement (Gu 1999). The authors reported that with IVD degeneration, the radial permeability of the annulus fibrosus decreased, mainly because of reduced water content. However, the axial and circumferential permeability coefficients increased, mainly due to structural change, leading to greater IVD isotropic permeability behavior (Gu 1999).

Sixty one percent of time in the work and home environment is spent in the standing posture (US Department of Labor, Bureau of Labor Statistics, 2016). Although prolonged weight bearing postures, such as standing and walking, have been associated with decreased spine height (Tyrrell 1985, Puntumetakul et al 2009), some studies reported that seated weight bearing postures could result in spine height gain (Magnusson 1996a). Sustained and repetitive lumbar extension postures frequently occur after periods of prolonged unloading such as sleep. These postures are periodically repeated throughout the day during activities such as standing and walking (US Department of Labor Bureau of Labor Statistics 2016).

People presenting with directional preferences that include lumbar

extension tend to respond well to exercises geared toward trunk extension (Stankovic 1990, Swinkels 2009, Oliveira 2012). Significant and rapid changes in central and distal pain intensity and location have resulted from standing end-range trunk extension in patients with low back and referred pain (Donelson 1991). Additional studies reported that standing back extension exercises resulted in back pain episodes' prevention and decreased back pain in care workers (Matsudaira 2015; Dunsford 2011). Standing exercises have the advantage to be functional and easily performed in work and home settings (Tonosu 2016).

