Our aim is to better understand the effect of standing sustained and repetitive trunk extensions on spinal height and LBP patients' symptoms intensity, centralization and function. With many patients commonly falling into a directional preference group and responding positively to mechanical spinal input, it is our aim to investigate if such trunk extension postures performed in standing affect spinal height in regard to growth or shrinkage and if these changes are associated with symptoms intensity, centralization and functional alterations.

Value(s):

No previous study has examined changes in spinal height following standing trunk extension postures and little is known on the effect of such standing postures on spinal height. The results of this study could impact rehabilitation programs that include standing trunk extension as a means of therapeutic intervention. This is valuable especially in aging population with degenerated IVD's, loss of IVD height and propensities toward spinal stenosis, as we do not know if those subjects with directional preferences toward spinal extension could use standing trunk extension postures at home or in the work

environment to grow and/or prevent spinal shrinkage.

RESEARCH QUESTIONS, HYPOTHESES AND VARIABLES

Research Question(s) (RQs)-This project aims to answer the following research questions:

1. **RQ 1:** Does sustained and repetitive standing trunk extension following a period of spinal loading effect spinal height, pain, centralization and function testing outcomes immediately and two weeks following the interventions in patients with LBP?
2. **RQ 2:** Following a period a spinal loading, is there a difference in spinal height, pain, centralization and function testing outcome *changes* immediately and two weeks following sustained and repetitive standing trunk extension postures in patients with LBP?
3. **RQ 3:** Is there a correlation between the degree of trunk extension during standing lumbar extension posture and spinal height, pain, centralization and function testing outcomes *changes* immediately and two weeks following the interventions in patients with LBP?

Research Hypotheses- (RH)This student has devised the following research hypotheses:

1. **RH 1:** It is expected that following a period of trunk loading, both sustained and repetitive trunk extension postures in standing will result in increased spinal height, reduced pain, enhanced centralization and

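### The hypothesis 3 correlation between degree of trunk extension and spinal height change is open to confounding by age; an adjusted estimate should be reported beside it.

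*Combined protocol and SAP*

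**What the plan says.** For hypothesis 3 the Data Analysis section reads: "Experimental hypothesis 3 will be tested with Pearson product-moment correlations to determine the strength of correlations between the degree of trunk extension" and changes in spinal height, pain and function. The abstract says the same: "Pearson product-moment correlations will be used to measure correlations between lumbar ROM in relation to spinal height and outcome measures". Centralization is handled by a Spearman correlation. No covariate, partial correlation, regression or stratification is planned for hypothesis 3, and the plan does not say whether the two arms are pooled.

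The hypothesis itself (RH 3) is worded as an association: "there will be a positive correlation between the degree of trunk extension during standing trunk extension posture and spinal height" and the other outcome changes.

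Randomisation (Testing Sequence, Session 1) assigns the type of extension, sustained or repetitive. It does not assign how far a subject extends, which is measured with inclinometers.

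On age, the inclusion criteria admit 18 to 80 years. Age is recorded but appears in Data Analysis only among the descriptive statistics. The Background says that "researchers have studied the IVD hydraulic permeability and the influence that age and/or degeneration have on fluid movement", and the Value(s) paragraph says of the expected results: "This is valuable especially in aging population with degenerated IVD's, loss of IVD height and propensities toward spinal stenosis".

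**The concern.** Randomisation protects the comparison of sustained with repetitive extension. It does not protect a correlation with the degree of extension, which is a characteristic the subject brings to the session. Any variable related both to extension and to height change will move that correlation. Age is a natural candidate here: the eligible range is wide, the plan's own Background ties age and/or degeneration to the fluid movement thought to lie behind height change, and the variable is already collected.

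What is at stake is the reading of the hypothesis 3 result for height. The Value(s) paragraph looks ahead to effects on rehabilitation programmes. That use depends on extension being related to height gain among people of similar age, and the planned r cannot separate this from an age gradient. The direction of any distortion is open: age could produce a correlation where none exists at fixed age, enlarge a real one, or hide it.

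**Working it through.** **No figure to reproduce.** The plan gives no target correlation, power, effect size or SD for hypothesis 3, and no derivation of its 40 completers.

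**Inputs from the documents.** n = 40 subjects completing both days (Subjects / Specimens); alpha = 0.05 (Data Analysis).

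**Assumed inputs.** A two-sided test (sidedness is not stated); both arms pooled in one test; no Bonferroni division (the plan applies it only as needed); approximately normal variables; and the two age correlations, a = corr(age, extension) and b = corr(age, height change).

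**Step 1: size of the induced correlation.** In general

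r(extension, height change) = a × b + p × √[(1 − a²)(1 − b²)],

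where p is the partial correlation at fixed age. If p = 0, the unadjusted r equals a × b.

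**Step 2: critical value.** r_crit = t / √(t² + df).
- Unadjusted, df = 38, t = 2.024: 2.024 / √(4.098 + 38) = 0.312.
- Adjusted for age, df = 37, t = 2.026: 2.026 / √(4.105 + 37) = 0.316.
- Adjusted for age and arm, df = 36, t = 2.028: 2.028 / √(4.113 + 36) = 0.320.

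**Step 3: chance of a significant unadjusted r when p = 0** (simulation, 40,000 to 50,000 trials per row, n = 40).

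| \|a\| / \|b\| | Induced \|r\| | Unadjusted test | Age-adjusted test |
|---|---|---|---|
| 0 / 0.5 | 0 | 5% | 5% |
| 0.2 / 0.2 | 0.04 | about 6% | 5% |
| 0.3 / 0.3 | 0.09 | 8-9% | 5% |
| 0.5 / 0.4 | 0.20 | 24% | 5% |
| 0.6 / 0.5 | 0.30 | 48% | 5% |

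A hand check for 0.5/0.4 with Fisher's z: atanh(0.312) = 0.323 and atanh(0.20) = 0.203, with standard error 1/√37 = 0.164. Then (0.323 − 0.203) / 0.164 = 0.73, an upper-tail probability of about 23%, close to the simulated 24%.

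For the induced r alone to equal the critical value, two equal links would each have to be √0.312 = 0.56.

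**Step 4: the masking direction.** Suppose a = −0.5, b = +0.4 and a real partial correlation p = 0.436, the value that the age-adjusted test detects with about 80% power at n = 40. The unadjusted r is then −0.20 + 0.436 × √(0.75 × 0.84) = −0.20 + 0.346 = 0.146. The unadjusted test finds the positive association in about 14% of trials; the age-adjusted test finds it in 81%.

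**Step 5: if the test is run within an arm (20 per arm assumed).** The unadjusted error rate is 7% at 0.3/0.3 and 19% at 0.5/0.5, against 8-9% and 35% when 40 subjects are pooled.

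**The case against.** The strongest objection is that confounding needs two links and the documents establish neither. Nothing says that extension range varies with age; with that link at zero the unadjusted test keeps its 5%. On the second link, the Background reports results for degeneration only, and they run in opposite directions: "the radial permeability of the annulus fibrosus decreased, mainly because of reduced water content", whereas "the axial and circumferential permeability coefficients increased, mainly due to structural change". The remark on ageing in the Value(s) paragraph concerns lost disc height, which is a level and not a response to extension. All of this stands. A reader might infer that younger discs recover more and that a positive result would therefore be spurious; the documents support neither that sign nor that direction of bias. The unknown sign does not remove the problem, though, because masking is as possible as mimicry.

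A second objection is that hypothesis 3 asks only for a correlation, which Pearson's r answers, and an age-driven correlation is still a true marginal one. That also stands. A reader might infer that the plan commits to reporting an age gradient as an effect of extension; it does not. The point is about how the result can be interpreted.

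Third, the larger error rates come from assumed correlations and one pooled test. That is correct, and at links of 0.3 or less the distortion is small.

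Fourth, the instruction to lean back to tolerance is on the home exercise sheets (Figures 6 and 7), and the in-clinic descriptions do not repeat it. It therefore cannot be used to say how far subjects extend when measured. The argument does not need it: it is enough that degree is not randomised.

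Fifth, age is not the only candidate. Body mass index, baseline pain and fear-avoidance scores are also recorded and unadjusted. Arm has a more direct basis, since RH 2 predicts a larger height gain with sustained extension. That is a good reason to include arm if the arms are pooled.

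Finally, using height change removes age differences in height level. It does not remove age differences in response.

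**Conclusion.** The point holds in a limited form. The planned analysis relates a non-randomised exposure to height change without adjustment, in a sample that may span 18 to 80 years, although age is recorded and the Background gives a reason to think it could matter. Whether the unadjusted r is in fact distorted, and in which direction, cannot be determined from the documents.

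The plausible size runs from nothing (5% if either link is zero) through minor (8-9% at 0.3/0.3) to serious (24% at 0.5/0.4, 48% at 0.6/0.5). These figures are conditional on the assumed links, 40 pooled subjects, a two-sided 0.05 test and no association at fixed age. This is an inexpensive improvement to a secondary, associational question. It has no bearing on the randomised comparison of the two arms under hypothesis 2.

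**What to change.** In the hypothesis 3 paragraph of Data Analysis, for spinal height change:

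- Keep the planned Pearson r and describe it as association only.
- Report beside it the partial correlation of extension with height change, or the regression of height change on extension, adjusted for age and, if the arms are pooled, for arm. State whether they are pooled.
- Base any statement that greater extension goes with greater height gain on the adjusted estimate.

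The cost is one sentence, with no new data or visits, and about one degree of freedom per term. At n = 40 the critical r goes from 0.312 to 0.316 with age and to 0.320 with age and arm. The correlation detectable with 80% power goes from 0.431 to 0.436 with age alone.

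Reporting the correlation of age with height change and its 95% confidence interval would be informative given the Value(s) paragraph, but it is optional: no research question asks for it, and leaving it out is not an error.

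### The correlations for research hypothesis 3 (RH3) ignore treatment arm and do not say which extension measurement they use; adjusting for arm is nearly free

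*Combined protocol and SAP*

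**What the plan says.** The Data Analysis section tests hypothesis 3 with "Pearson product-moment correlations to determine the strength of correlations between the degree of trunk extension during standing trunk extension posture" and changes in height, pain and function. A separate Spearman correlation is to "determine the strength of the correlation between centralization and the degree of trunk extension posture in standing". The Abstract gives the extension analysis in shorter form: "Pearson product-moment correlations will be used to measure correlations between lumbar ROM in relation to spinal height and outcome measures". None of these sentences mentions arm, either as a stratum or as an adjustment.

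The Abstract plans one correlation by group, but for another pair of variables: the "relationship between spinal height changes and changes of pain and location of symptoms for each group". Extension is not part of it.

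RH2 predicts that "sustained standing trunk extension posture in standing will result in greater spinal height gain as compared to repetitive standing trunk extension postures", and that "repetitive standing trunk extension postures will result in greater improvements in pain, centralization and function testing outcomes". It makes no prediction about degree of extension. RH3 predicts a positive correlation between extension and the change in every outcome.

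Under Testing Sequence, extension is measured with inclinometers before and after the intervention in each session, giving four readings per patient. The session text links the post-intervention reading to the correlations. The Data Analysis section does not say whether that reading or the initial one is used, or from which session.

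**The concern.** In a two-arm trial, a correlation over all patients combines two things: the association among patients who had the same manoeuvre, and the difference between the arms' averages. RH3 asks about the first. If both extension and outcome change differ by arm, the second enters the coefficient and can produce a correlation where none exists within arm, or cancel one that does.

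The setting makes this worth guarding against. RH2 expects the arms to differ on the outcomes. The post-intervention extension readings follow different manoeuvres, and the session 2 readings also follow about two weeks of different home exercise. The Background treats static and repeated postures as alternative ways of increasing spinal range of motion and leaves open which is better. At stake is the conclusion on one of the three stated hypotheses.

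**Working it through.** **Inputs from the documents.** 40 patients completing both days (Subjects / Specimens); two arms (Testing Sequence); alpha 0.05 (Data Analysis).

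**Assumptions.** 1:1 allocation, so 20 per arm, and two-sided tests; neither is stated. The documents give no effect sizes or SDs, so every standardized difference below is assumed. They also give no power or detectable correlation for RH3, so there is no planned figure to reproduce.

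**Formula.** Let rho be the common within-arm correlation, and dx and dy the arm differences in extension and in outcome change, in within-arm SDs. For two equal arms:

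r(unadjusted) = (rho + dx·dy/4) / √[(1 + dx²/4)(1 + dy²/4)]

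**Step 1: RH2's differences alone (dx = 0).** The formula reduces to rho/√(1 + dy²/4). If rho = 0, the result is exactly 0 for any dy. If rho = 0.3 and dy = 0.8, it is 0.3/√1.16 = 0.279.

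**Step 2: extension also differs, same direction, rho = 0.** With dx = dy = 0.5, r = 0.0625/1.0625 = 0.059. With dx = dy = 0.8, r = 0.16/1.16 = 0.138.

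**Step 3: extension differs in the opposite direction, rho = 0.3.** With dx = −0.8 and dy = 0.8, r = (0.3 − 0.16)/1.16 = 0.121.

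**Step 4: rejection rates.** Simulation of 20,000 trials per row, comparing the plain Pearson test (38 df, critical |r| 0.312) with the partial correlation given arm (37 df, critical |r| 0.316):

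| rho | dx | dy | Unadjusted r (formula) | Unadjusted rejection | Adjusted rejection |
|---|---|---|---|---|---|
| 0 | 0 | 0.8 | 0 | 4.9% | 5.0% |
| 0 | 0.5 | 0.5 | 0.059 | 6.6% | 4.9% |
| 0 | 0.8 | 0.8 | 0.138 | 13.9% | 5.2% |
| 0.3 | 0 | 0.5 | 0.291 | 45.3% | 46.8% |
| 0.3 | 0 | 0.8 | 0.279 | 42.1% | 46.7% |
| 0.3 | 0 | 1.2 | 0.257 | 36.2% | 46.9% |
| 0.3 | −0.5 | 0.8 | 0.180 | 19.1% | 46.6% |
| 0.3 | −0.8 | 0.8 | 0.121 | 10.2% | 46.4% |

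A separate run of 40,000 trials gave 6.4% and 13.5% for the two false-positive rows with dx = dy = 0.5 and 0.8.

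**Step 5: price of the alternatives.** By Fisher's z, the correlation detectable with 80% power is tanh[(1.960 + 0.842)/√(n − 3 − k)], with k the number of adjusting variables:

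- Unadjusted, n = 40: tanh(2.802/√37) = 0.431.
- Adjusted for arm, n = 40: tanh(2.802/√36) = 0.436.
- One arm alone, n = 20: tanh(2.802/√17) = 0.591. Simulated power at r = 0.3 is about 25%.

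**Step 6: direction depends on coding.** If change is coded as improvement, RH2 has height favouring sustained and symptoms favouring repetitive, so any one non-zero dx pushes the height and symptom correlations opposite ways. If NPRS, Oswestry and symptom location are left as raw follow-up minus baseline, the sustained arm would be higher on height change and also higher (less reduced) on symptoms, and the push is in the same direction. The plan does not state the coding.

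**The case against.** A reader might infer that the arm differences RH2 predicts are enough to create or hide an RH3 correlation. The documents do not support that. RH2 concerns outcomes only, and Step 1 shows that outcome differences alone leave a null correlation at zero and cost a real one little. An arm difference in extension is also needed.

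The documents give reasons not to expect a large one. Figure 3 uses one posture for the sustained position and the repetitive end position. Both home sheets ask patients to lean back as far as they can tolerate. Intervention times are matched. For the session 1 reading before the intervention, randomization makes the expected difference zero. This stands, and it is why figures based on differences of 1 SD or more should not be relied on. It does not exclude a difference after the intervention or at session 2.

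Two further inferences should be resisted. RH3's reference to patients with low back pain does not prescribe pooling: RQ2, which compares the arms, uses the same phrase. And the Abstract's by-group Spearman correlation does not contradict the RH3 plan, because it pairs height change with pain and location change. The plan is silent on arm, not inconsistent.

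Finally, RH3 is the third hypothesis and correlational. That bears on severity, but not on whether adjustment is better.

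**Conclusion.** The point holds as a minor one. The RH3 correlations have no term for arm, and the extension measurement is not identified. That second gap largely decides whether arm can matter: not in expectation for the session 1 pre-intervention reading, possibly for the others.

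RH2's outcome differences alone give only slight dilution (0.30 to about 0.28 at 0.8 SD). If extension also differs by arm, the false-positive rate rises to about 6.5% or 13.5% at 0.5 or 0.8 SD on both variables. With opposite 0.8 SD differences, power at a within-arm r of 0.3 falls from about 47% to about 10%. These figures rest on assumed differences, 20 per arm, two-sided testing and a common within-arm correlation. They show what could happen, not what is expected. The arm-adjusted analysis keeps its error rate at about 5% in every scenario tried, so the case for it does not depend on which scenario is true.

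**What to change.** Amend the hypothesis 3 paragraph of Data Analysis, and the matching Abstract sentence, as follows:

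- Make the partial correlation adjusted for arm the RH3 analysis, with a rank-based partial correlation for centralization, each with a 95% confidence interval. The estimate describes association across patients within arm.
- Name the extension measurement used (before or after the intervention, and which session) for each outcome change.
- Code change as improvement for NPRS, Oswestry and symptom location. Higher scores mean more pain, worse function and more distal symptoms respectively, so otherwise the positive correlation that RH3 predicts has no single meaning.
- Show arm-specific coefficients and scatterplots as descriptive only. They let a reader judge whether a common within-arm correlation is reasonable, but 20 per arm gives only about 25% power at r = 0.3.

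The cost is a few sentences and one degree of freedom: the correlation detectable with 80% power moves from 0.431 to 0.436. No extra patients or measurements are needed.
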